CDC-defined high risk for severe COVID-19(1)	-Descriptive (any high-risk condition and for each individual condition) -Covariate (each individual condition)	 Assessed using all available lookback data. Asthma Cancer, as hematologic malignancies Cerebrovascular disease Chronic kidney disease: people receiving dialysis Chronic lung diseases: bronchiectasis, COPD, interstitial lung disease, pulmonary embolism, pulmonary hypertension Chronic liver diseases: cirrhosis, non-alcoholic fatty liver disease, alcoholic liver disease, autoimmune hepatitis Cystic fibrosis Diabetes mellitus, type 1 Diabetes mellitus, type 2 Disabilities, including Down syndrome Heart conditions: heart failure, coronary artery disease, or cardiomyopathies HIV Mental health conditions: mood disorders including depression; Schizophrenia spectrum disorders Neurologic conditions limited to dementia Obesity (BMI ≥30 kg/m²) Primary immunodeficiencies Smoking, current and former Solid organ or blood stem transplantation Tuberculosis Use of corticosteroids or other immunosuppressive medications The lists of codes are provided in the Protocol Annex. Note: due to the limitations of claims data, "physical inactivity" will not be measurable and has been removed from the list.

Variable	Role(s)	Operational definition
Charlson Comorbidity Index using weights from Quan et al (2011)	-Descriptive (continuous and categorical) -Covariate (categorical)	Assessed in 6 months prior to index date. Conditions are scored as: 1 point for each of: • Chronic pulmonary disease • Rheumatologic disease • Diabetes mellitus with chronic complications • Renal disease 2 points for each of: • Congestive heart failure • Dementia • Mild liver disease • Any malignancy, including leukemia and lymphoma 4 points for each of: • Moderate or severe liver disease • HIV/AIDS 6 points for each of: • Metastatic solid tumor Categorized as: 0, 1 or 2+
Receipt of skilled nursing care and/or long-term care facility stay in year prior to index	-Descriptive -Covariate	Categorized as: 0, 1 or 2+ The list of codes is provided in the Protocol Annex Assessed in 6 months prior to index date Yes or No The list of codes is provided in the Protocol Annex
Wellness visit	-Descriptive -Covariate	Assessed in 6 months prior to index date Yes or No The list of codes is provided in the Protocol Annex
Decreased functional status	-Descriptive -Covariate	Assessed in 6 months prior to index date Yes or No The list of codes is provided in the Protocol Annex

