Variable	Role(s)	Operational definition		
Influenza vaccination in 6 months prior to index	-Descriptive -Covariate	Assessed in 6 months prior to index Yes or No The list of codes is provided in the Protocol Annex		
Pneumococcal vaccination using all-available time prior to index	-Descriptive -Covariate	Assessed using all-available lookback data Yes or No The list of codes is provided in the Protocol Annex		
Herpes zoster vaccination using all-available time prior to index	-Descriptive -Covariate	Assessed using all-available lookback data Yes or No The list of codes is provided in the Protocol Annex		
Outpatient visits prior to index	-Descriptive (continuous and categorical) -Covariate (categorical)	Number of outpatient visits in 180 days prior to index Categorized as: 0, 1 or 2+ The list of codes is provided in the Protocol Annex		
Inpatient admissions prior to index	-Descriptive (continuous and categorical) -Covariate (categorical)	Number of inpatient admissions in 180 days prior to index Categorized as: 0, 1 or 2+ The list of codes is provided in the Protocol Annex		
Emergency department visits prior to index	-Descriptive (continuous and categorical) -Covariate (categorical)	Number of emergency department visits in 180 days prior to index Categorized as: 0, 1 or 2+ The list of codes is provided in the Protocol Annex		
Telehealth visits prior to index	-Descriptive (continuous and categorical) -Covariate (categorical)	Number of telehealth encounters (CPT: 99201-99215) in 180 days prior to index Categorized as: 0, 1 or 2+		
Number of documented SARS-CoV-2 tests in the 180 days prior to index	-Descriptive (continuous and categorical) -Covariate (categorical)	Number of visits in any setting with CPT in 180 days prior to index: 86408, 86409, 0225U, 0226U Categorized as: 0, 1 or 2+		
Prior post- COVID-19 conditions	-Descriptive -Covariate	Assessed using all-available lookback data, any encounter regardless of setting with ICD- 10-CM U09.9 "Post-COVID-19 condition" Yes or No		

Variable	Role(s)	Operational definition
Prior COVID-19 diagnosis	-Descriptive -Covariate	Any encounter with ICD-10-CM code: U07.1 between 90 and 365 days prior to index Yes or No
Prior bivalent BA.4/5 COVID-19 vaccine	-Descriptive -Subgroup	Where the BNT162b2 XBB.1.5 vaccine is the exposure of interest. Using all-available lookback data, received bivalent BA.4/5 COVID-19 vaccine (regardless of brand) prior to index Yes or No The list of codes is provided in the Protocol Annex

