5.3.3. Covariates

The list of demographic and clinical characteristics that will be used to describe the cohort and considered for inclusion as covariates in models are provided in Table 5.3. Age, sex, state of residence and prior COVID-19 vaccinations will be obtained from the HealthVerity claims database and state vaccine registries. The HealthVerity claims database will be the sole source of all other variables.

All covariates will be assessed on or prior to index date and will therefore be considered as time-fixed variables during the follow-up. Categories may be collapsed or covariates may be excluded or combined if models fail to converge or if patient counts are low (Section 5.7.2). Additionally, categories with large patient counts may be split further.

Table 5.3 Demographic and Clinical Characteristics

Variable	Role(s)	Operational definition
Age	-Inclusion/ exclusion	Age assessed at index date.
	criteria	Categorized as: 18-49, 50-64 or 65+ years.
	-Descriptive	
	(continuous and	
	categorical)	
	-Covariate	
	(categorical)	
	-Subgroup	
	(categorical)	
Sex	-Inclusion/ exclusion	Sex assessed at index date.
	criteria	Male, female or unknown.
	-Descriptive	
	-Covariate	
State of residence	-Inclusion/ exclusion	Defined in Section 5.2
	criteria	California or Louisiana
	-Descriptive	
	-Covariate	
	-Subgroup	
Payor	-Descriptive	Payor assessed at index date.
	-Covariate	Commercial, Medicaid, Medicare Advantage,
		Unknown, Missing

Variable	Role(s)	Operational definition
CDC-defined high	-Descriptive (any	Assessed in the year prior to index
risk for severe	high-risk condition	• Age ≥ 50 years
COVID-19 ²	and for each	Asthma
	individual condition)	Cancer, as hematologic malignancies
	-Covariate (each	Cerebrovascular disease
	individual condition except age ≥ 50 years)	Chronic kidney disease: people receiving dialysis
		Chronic lung diseases: bronchiectasis,
		COPD, interstitial lung disease, pulmonary
		embolism, pulmonary hypertensionChronic liver diseases: cirrhosis, non-
		alcoholic fatty liver disease, alcoholic liver
		disease, autoimmune hepatitis
		Cystic fibrosis
		Diabetes mellitus, type 1
		Diabetes mellitus, type 2
		Disabilities, including Down syndrome
		Heart conditions: heart failure, coronary
		artery disease, or cardiomyopathiesHIV
		Mental health conditions: mood disorders
		including depression; Schizophrenia
		spectrum disorders
		Neurologic conditions limited to dementia
		Obesity (BMI ≥30 kg/m²)
		Primary immunodeficiencies

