		Annex
Pneumococcal	-Descriptive	Assessed in the year prior to index
vaccination using	-Covariate	Yes or No
all-available time		The list of codes is provided in the Protocol
prior to index		Annex
Herpes zoster	-Descriptive	Assessed in the year prior to index
vaccination using	-Covariate	Yes or No
all-available time		The list of codes is provided in the Protocol
prior to index		Annex
Outpatient visits	-Descriptive	Number of outpatient visits in 365 days prior
prior to index	(continuous and	to index
	categorical)	Categorized as: 0, 1 or 2+
	-Covariate	The list of codes is provided in the Protocol
	(categorical)	Annex, and includes office/clinic visits as well
		as telehealth.
Inpatient	-Descriptive	Number of inpatient admissions in 365 days
admissions prior to	(continuous and	prior to index
index	categorical)	Categorized as: 0, 1 or 2+
	-Covariate	The list of codes is provided in the Protocol
Г	(categorical)	Annex
Emergency	-Descriptive	Number of emergency department visits in
department visits	(continuous and	365 days prior to index
prior to index	categorical) -Covariate	Categorized as: 0, 1 or 2+
		The list of codes is provided in the Protocol Annex
Telehealth visits	(categorical) -Descriptive	Number of telehealth encounters (CPT:
prior to index	(continuous and	99201-99215) in 365 days prior to index
prior to macx	categorical)	Categorized as: 0, 1 or 2+
	-Covariate	Categorized as. 0, 1 of 2
	(categorical)	
Number of	-Descriptive	Number of visits in any setting with CPT in
documented	(continuous and	365 days prior to index: 86408, 86409, 0225U,
SARS-CoV-2 tests	categorical)	0226U
in the 180 days	-Covariate	Categorized as: 0, 1 or 2+
prior to index	(categorical)	
Prior post-	-Descriptive	Assessed in the year prior to index, any
COVID-19	-Covariate	encounter regardless of setting with ICD-10-
conditions		CM U09.9 "Post-COVID-19 condition"
		Yes or No

Variable	Role(s)	Operational definition
Prior COVID-19	-Descriptive	Any encounter with ICD-10-CM code: U07.1
diagnosis	-Covariate	between 90 and 365 days prior to index
		Yes or No
Prior bivalent	-Descriptive	Where the BNT162b2 XBB.1.5 vaccine is the
BA.4/5 COVID-19	-Subgroup	exposure of interest. Using all-available
vaccine		lookback data, received bivalent BA.4/5
		COVID-19 vaccine (regardless of brand) prior
		to index
		Yes or No
		The list of codes is provided in the Protocol

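### Prior outpatient visits enter both vaccine-effectiveness models as 0, 1 or 2+ by default, with finer splitting left optional; a finer form should be pre-specified, mainly for Aim 1

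*SAP*

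**What the plan says.** Table 5.3 of the Aim 2 SAP (section 5.3.3) defines the covariate as "Number of outpatient visits in 180 days prior to index Categorized as: 0, 1 or 2"; the source follows this with a plus sign, so the top category is open-ended. Its role is listed as "Descriptive (continuous and categorical) -Covariate (categorical"): the count is held and tabulated as a continuous variable, but the model uses the categories. Inpatient, emergency department (ED) and telehealth visits and SARS-CoV-2 tests are coded the same way.

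Table 5.3 of the Aim 1 SAP reads "Number of outpatient visits in 365 days prior" to index, again "Categorized as: 0, 1 or 2" or more, and states that office, clinic and telehealth contacts all count.

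Protocol Table 5 lists outpatient visits as a number over 180 days and sets no categories. Section 5.3.3 of each VE SAP adds that "categories with large patient counts may be split further". Neither SAP says when that would be done, at which cut-points, or whether before results are seen.

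**The concern.** The primary outcome in Aims 1 and 2 is any encounter carrying the COVID-19 code, so a person must use care to become a case. Section 8 of the protocol, in discussing the test-negative design, itself notes an association between vaccination and healthcare seeking. Prior visit count is therefore a plausible common cause of exposure and of outcome ascertainment.

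With 0, 1 or 2+ coding, a person with 2 visits and a person with 25 fall in the same stratum. Any gradient of vaccination and diagnosis within that stratum goes unadjusted by this variable. Aim 1 is the more exposed: its window is twice the protocol's, its definition is broad, and the top category still starts at 2. If care-seeking raises both vaccination and diagnosis, the bias pushes the hazard ratio towards or above 1 and lowers VE. With the planned sample sizes, a bias of a few points could matter for common outcomes, where the intervals are very narrow.

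**Working it through.** **1. The plan's own figures.** Doses: 0.75 × 12 million × 0.16 × 0.60 = 864,000 adults; 0.25 × 12 million × 0.16 × 0.60 = 288,000 children. Both match the SAPs. BNT162b2 uptake is 0.16 × 0.60 = 9.6%.

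Table 5.4 was re-derived by expected-value integration of the time-varying Cox model, with incidence as rate times time. For 3 million at VE 20% and 10,000 cases per 100,000 this gives 19 to 21 with 274,517 events, against the stated 19 to 21 with 274,706. The match needs 16% uptake. At 9.6% the full-sample limits in the 10,000 and 1,000 columns move by at most about one point in the cells checked.

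Stated half-widths at VE 30%, as (upper − lower)/2:

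| Cases per 100,000 | Aim 1, 8.55 million | Aim 2, 3 million |
|---|---|---|
| 10,000 | (31 − 29)/2 = 1 | (31 − 29)/2 = 1 |
| 1,000 | (32 − 28)/2 = 2 | (34 − 26)/2 = 4 |
| 100 | (36 − 22)/2 = 7 | (41 − 17)/2 = 12 |
| 50 | (40 − 20)/2 = 10 | (45 − 11)/2 = 17 |

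**2. Assumptions for the bias.** Apart from the 9.6% uptake, none of these inputs is in the documents.
- Visits v are negative binomial with mean m and dispersion 1, so P(0) = 1/(1+m), P(1) = m/(1+m)² and P(2+) = m²/(1+m)².
- Vaccination odds and the coded-COVID rate both rise as (1+v)^e, with e = 0.3 (moderate) or 0.5 (strong).
- True hazard ratio 0.70. Visits are the only confounder.

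**3. Calculation.** The adjusted ratio is the Mantel-Haenszel rate ratio over visit strata s: Σ(E1s·N0s/Ts) / Σ(E0s·N1s/Ts), where E is expected events, N is people by vaccination status and Ts = N1s + N0s. VE read = 100 × (1 − ratio). Example, m = 6, e = 0.5: the crude bias factor is 1.210 and the factor after 0/1/2+ adjustment is 1.102, so VE reads 100 × (1 − 0.70 × 1.102) = 22.9 (22.8 unrounded).

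| Mean visits | In 2+ | VE read, e = 0.3 | VE read, e = 0.5 |
|---|---|---|---|
| 1 | 25% | 29.8 | 29.2 |
| 2 | 44% | 29.3 | 27.6 |
| 4 | 64% | 28.4 | 24.9 |
| 6 | 74% | 27.7 | 22.8 |
| 8 | 79% | 27.1 | 21.3 |

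At means of 4 to 8, 0/1/2+ leaves 35% to 58% of the visit-count confounding on the log scale. Bands of 0, 1, 2-3, 4-6, 7-12 and 13+ bring VE back to 28.8 to 29.9.

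**4. Wider assumptions.** A separate grid with true VE 20%, mean visits 0.5 to 8 and other association shapes left 3% to 61% of the visit-count confounding. Estimated VE ran from 20.0% down to 6.0%.

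**5. Against precision.** At means of 4 to 8 the bias is 1.6 to 2.9 points (moderate) or 5.1 to 8.7 points (strong). All of these exceed the 1-point half-width at 10,000 per 100,000. At 1,000 per 100,000 in Aim 1 (half-width 2) the moderate case straddles the half-width. At 50 per 100,000 even 8.7 points is below the Aim 1 half-width of 10. At means of 1 to 2, which may suit Aim 2's 180 days better, the bias is 0.2 to 2.4 points.

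**The case against.** **Care-seeking is covered elsewhere.** A reader might infer that it enters the models only through 0/1/2+ visits. The documents do not support that. The models also take entries such as "Wellness visit -Descriptive -Covariate" and "Influenza vaccination in 6 months prior to index" (one year in Aim 1), pneumococcal and zoster vaccination, payor, each high-risk condition, the Charlson index, long-term care and prior COVID-19 diagnosis. These would absorb part of the bias, and this objection stands. How much is unknown. Adding a yes/no wellness flag to the calculation, with an assumed 25% chance that any visit is a wellness visit, moves VE at means of 4 to 8 only to 28.7-27.6 (moderate) or 25.7-22.9 (strong).

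**The split clause may be used.** A 2+ group holding most of a multi-million cohort is the situation it describes, so it is not established that the coarse coding will be run. What remains is that the choice is open and could be made after results are seen.

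**Negative controls are planned.** Section 5.7.6 of each VE SAP runs the same analysis on outcomes that also require an encounter, with optional bias correction. This can detect such bias, but only after the fact, and the adjustment that would follow is not specified.

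**The size is not established.** A reader might infer that most care-seeking confounding stays uncontrolled, or that the bias exceeds the confidence interval width in general. Neither follows: the inputs are assumed, the range starts at negligible, and the intervals for rare outcomes are wider than the bias.

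**The other counts.** A reader might want every utilization count re-coded. For rare counts (assumed mean 0.4) the same calculation gives a bias of about 0 to 0.1 point.

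**Conclusion.** The point holds as a pre-specification weakness: the default coding of outpatient visits is coarse in both VE SAPs, and refinement is discretionary. It matters mainly in Aim 1 and for common outcomes. The likely direction is downward, provided care-seeking raises both vaccination and diagnosis. The size runs from negligible to several VE points and depends on a visit distribution and association strengths that the documents do not give. Because visits are the sole confounder in the calculation, its figures are upper bounds for the inputs used, not estimates of the bias in the planned model. This is a cheap improvement, not a defect that invalidates the analysis.

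**What to change.** In Table 5.3 of both VE SAPs, for the primary outcome and any outcome that meets the rule of five events per degree of freedom, pre-specify outpatient visits as a restricted cubic spline of log(1 + count) or as bands such as 0, 1, 2-3, 4-6, 7-12 and 13+. Keep 0/1/2+ as the stated fallback for sparse outcomes. Re-coding ED, inpatient and test counts is optional.

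Cost: six bands use 5 degrees of freedom against 2 now, so 3 more, or 3 × 5 = 15 further events. At VE 30%, Table 5.4 expects 1,429 events (Aim 2) and 4,104 (Aim 1) even at 50 per 100,000. No new data are needed; the model specification becomes slightly longer.

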5.4. Data Sources

The sources of the data are the State of California and the State of Louisiana vaccine registries linked to closed claims in HealthVerity.

5.4.1. California and Louisiana Immunization Registries

The California Immunization Registry is run by the California Department of Public Health and collects nearly all records of COVID-19 vaccinations administered in the state of California.

Data include a unique HealthVerity person identification code, vaccination event date and Clinical Vaccines Administered (CVX) code. CVX codes are unique to brand and formulation of vaccine.

Data is linked using HealthVerity's tokenization software, whereby specific patient identifiers are passed through the software and a de-identified patient ID is assigned. The same tokenization process is applied to closed claims sourced by HealthVerity, and patients can thus be linked across data sources. The tokenization process occurs outside of Pfizer, no personal identifying information will be transferred, and Pfizer will only have access to de-identified data. The data comply with Health Insurance Portability and Accountability Act (HIPAA) regulations.

The Louisiana Vaccine Registry is structured and accessed in the same way as California.

5.4.2. HealthVerity's Administrative Claims Data

HealthVerity closed claims will be limited to approximately 19 million patients residing in California and approximately 3.8 million in Louisiana.

HealthVerity's description of their data is that they are generally representative of the age and sex distribution of the population. For our specific research context, samples created from HealthVerity claims also generally follow California's demographic patterns with respect to age & sex.

The California subset of HealthVerity does not include patients in the Kaiser Permanente network. Insurers contributing to closed claims in both states include a mix of commercial payers, Medicare Advantage/Part C pains, and Medicaid Managed Care plans. Data elements include patient demographic information, inpatient/outpatient visit-level information such as diagnoses, procedures, and length of stay, hospital characteristics, and medication information. Owing to the nature of claims, the data represent the final set of diagnoses over the course of the hospitalization sent to the patient's insurer for reimbursement, with diagnosis prioritization assigned by clinicians or hospital staff. For inpatient encounters, the data will be assumed to represent the overarching events during hospitalization and may be less subject to rule out diagnosis codes than electronic health record data.

BNT162b2 (COVID-19 vaccine formulations)
C4591065 NON-INTERVENTIONAL STUDY STATISTICAL ANALYSIS PLAN FOR SECONDARY DATA
COLLECTION STUDY
SAP version 1.0, 10 June 2024

Death information is available and is sourced from over 40,000 public and private sources nationally. The coverage rate, estimated at over 90% of CDC reported deaths through present day, is based on the number of deaths in the Fact of Death Mortality Index compared to the number of deaths reported by the CDC. Due to HIPAA privacy restrictions, date of death is reported as month and year. Cause of death is not available.

5.5. Sample Size and Power Calculations

Since the current study utilizes retrospective deidentified data without ability to recruit to a target, sample size calculations are not applicable. Further, this is a descriptive study without a priori specified hypotheses. However, we examined the precision of the expected XBB.1.5 absolute VE estimates for the outcomes under various scenarios.

(25% of 12 million are pediatric)*(16% uptake)*(60% of doses were Pfizer-BioNTech)

~ 288,000 pediatric XBB doses in California.

The sample size used at start of follow-up was 3 million. Assuming similar absolute VEs to those seen with the BA.4/5 vaccine for symptomatic COVID-19 infections, we could anticipate estimates between 20 and 40%[4]. To assess the precision for a range of outcomes, incidence rates of 50, 100, 1000 and 10,000 cases per 100,000 unvaccinated persons during the study period were considered. A censoring rate of 5% by the end of the study period was used. A uniform vaccination rate between 14 days after study index and the end of follow-up was assumed.

Survival and censoring times were simulated assuming exponential distributions. Vaccination status was modelled as a time-varying covariate[5]. Hazard ratios were input as 1-(VE/100). Simulations were run a minimum of 10 times per scenario. Cox regression models were run on each simulated dataset to estimate the 95% CIs for the log HRs. Means were generated and exponentiated to obtain the 95% CIs for the VEs using (1- HR) x 100 and used to describe VE precision. Simulations were repeated on 25% of the initial sample size to represent the precision in a potential subgroup.

Table 5.4 Simulated 95% Confidence Intervals [Total Number of Events] for BNT162b2 XBB.1.5 Vaccine Effectiveness Estimates

Number at Start of	Vaccine Effectiveness,	Cases per 100,000 Unvaccinated Persons by End of Study			
Follow-up	%	50	100	1000	10,000
3,000,000	20	2, 37 [1488]	7, 32 [2871]	16, 24 [28,678]	19, 21 [274,706]
Ī	30	11, 45 [1429]	17, 41 [2849]	26, 34 [28,475]	29, 31 [272,600]
	40	22, 53 [1418]	29, 51 [2845]	37, 43 [28,256]	39, 41 [270,864]
750,000	20	-24, 49 [361]	-7, 43 [720]	12, 28 [7150]	17, 23 [68,646]
[30	-12, 57 [358]	2, 50 [713]	22, 37 [7097]	28, 32 [68,173]
	40	6, 67 [354]	14, 58 [712]	33, 47 [7077]	38, 42 [67,719]

Table 5.4 shows that there should be sufficient sample size in the California registry to produce 95% CIs for VEs that exclude 0 for the evaluated VEs and incidence rates, except for the rarer event scenarios in a subgroup. Assuming similar VEs in the two state registries, the inclusion of patients from the Louisiana registry would increase the precision further.

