8.5. Study Size

Since the current study utilizes retrospective deidentified data without ability to recruit to a target, sample size calculations are not applicable. Further, this is a descriptive study without *a priori* specified hypotheses.

Initial data feasibility work has revealed approximately 19 million persons in the state of California with claims available in HealthVerity, among which approximately 25% are pediatric and 75% adult. Among these, approximately 12 million have at least one year of continuous medical and pharmacy enrollment. By end of 2023, we expect to have finished contracting to add approximately 565,000 additional persons. The proportion of these additional persons who will have 1-year continuous enrollment, and therefore the sample size estimates below have taken the conservative approach to not yet include these people.

We have identified 63% of persons in the claims data have at least one COVID-19 vaccine, and 16% received at least one bivalent dose. The claims population we have is not a random sample of Californians and may differ from the state's population in systematic ways (e.g. the age distribution). While differences may exist, we have high confidence in our ability to represent vaccination status for the individuals in our claims population.

We expect to begin to see XBB doses in data delivered in November 2023. Assuming uptake similar to that seen with the BA.4/5 vaccine, and non-differential uptake by age groups, we could anticipate in California:

(25% of 12 million are pediatric)*(16% uptake)*(60% of doses were Pfizer-BioNTech)

~ 288,000 pediatric XBB doses in California

(75% of 12 million are adult)*(16% uptake)*(60% of doses were Pfizer-BioNTech)

~ 864,000 adult XBB doses in California

Additional doses will be observed in Louisiana. In order to maintain patient de-identification, outcomes, covariates and subgroups will have at least 10 people in each category for inclusion in outputs. Throughout the protocol, this is referred to as "If sample size allows".

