5.5. Sample Size and Power Calculations

Since the current study utilizes retrospective deidentified data without ability to recruit to a target, sample size calculations are not applicable. Further, this is a descriptive study without a priori specified hypotheses. However, we examined the precision of the expected XBB.1.5 absolute VE estimates for the outcomes under various scenarios.

Assuming uptake similar to that seen with the BA.4/5 vaccine, and non-differential uptake by age groups, we could anticipate in California:

(75% of 12 million are adult)*(16% uptake)*(60% of doses were Pfizer-BioNTech)

~ 864,000 adult XBB doses in California

Among these 9 million adults, 95% were assumed to be non-immunocompromised and used as the sample size at start of follow-up. Assuming similar absolute VEs to those seen with the BA.4/5 vaccine for symptomatic COVID-19 infections, we could anticipate estimates between 20 and 40%. To assess the precision for a range of outcomes, incidence rates of 50, 100, 1000 and 10,000 cases per 100,000 unvaccinated persons during the study period were considered. A censoring rate of 5% by the end of the study period was used. A uniform vaccination rate between 14 days after study index and the end of follow-up was assumed.

Survival and censoring times were simulated assuming exponential distributions. Vaccination status was modelled as a time-varying covariate. Hazard ratios were input as 1-(VE/100). Simulations were run a minimum of 10 times per scenario. Cox regression models were run on each simulated dataset to estimate the 95% CIs for the log HRs. Means were generated and exponentiated to obtain the 95% CIs for the VEs using (1- HR) x 100 and used to describe VE precision. Simulations were repeated on 25% of the initial sample size to represent the precision in a potential subgroup.

Table 5.4 Simulated 95% Confidence Intervals [Total Number of Events] for BNT162b2 XBB.1.5 Vaccine Effectiveness Estimates

Number at Start of	Vaccine Effectiveness,	Cases per 1	00,000 Unvacci Stu		s by End of
Follow-up	%	50	100	1000	10,000
8,550,000	20	7, 29 [4116]	12, 27 [8242]	18, 23 [81,702]	19, 21 [782,794]
	30	20, 40	22, 36	28, 32	29, 31
	40	[4104] 30, 49	[8144]	[81,108] 38, 42	[777,275] 39, 41
		[4019]	[8095]	[80,490]	[771,141]
2,137,500	20	-3, 39 [1026]	4, 34 [2072]	15, 24 [20,348]	18, 21 [195,697]
	30	10, 49 [1022]	14, 42 [2042]	25, 34 [20,297]	28, 31 [194,371]
	40	20, 57 [1016]	27, 52 [2022]	36, 44 [20,104]	39, 41 [192,827]

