Table 5.4 shows that there should be sufficient sample size in the California registry to produce 95% CIs for VEs that exclude 0 for the evaluated VEs and incidence rates, except for the rare event scenario in a subgroup. Assuming similar VEs in the two state registries, the inclusion of patients from the Louisiana registry would increase the precision further.

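### Table 5.4 in the Aim 1 and Aim 2 SAPs cannot be reproduced from 9.6% BNT162b2 uptake with the stated vaccination timing, and the vaccinated fraction simulated is never given

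*SAP*

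**What the plan says.** Protocol 8.5 (Study Size) reports that, in the claims population, "16% received at least one bivalent dose". This is uptake of any brand, because the 60% Pfizer-BioNTech share is applied afterwards.

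The Aim 2 SAP, section 5.5, multiplies out "25% of 12 million are pediatric)*(16% uptake)*(60% of doses were Pfizer-BioNTech" to reach about 288,000 doses and starts the simulation with 3 million children. The Aim 1 SAP, section 5.5, uses "75% of 12 million are adult)*(16% uptake)*(60% of doses were Pfizer-BioNTech" to reach about 864,000 doses and adds: "Among these 9 million adults, 95% were assumed to be non-immunocompromised and used as the sample size at start of follow-up". That gives 8.55 million.

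Both SAPs then list the simulation inputs: VE of 20, 30 and 40%; 50 to 10,000 cases per 100,000 unvaccinated; 5% censoring; exponential event and censoring times; and "A uniform vaccination rate between 14 days after study index and the end of follow-up was assumed". On replicates they say "Simulations were run a minimum of 10 times per scenario".

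From Table 5.4 the Aim 2 SAP concludes that the California data should "produce 95% CIs for VEs that exclude 0 for the evaluated VEs and incidence rates, except for the rarer event scenarios in a subgroup". The Aim 1 SAP draws the same conclusion, "except for the rare event scenario in a subgroup". In both SAPs the exposure is BNT162b2 XBB.1.5 only (section 5.3.1).

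**The concern.** The precision of a hazard ratio for a time-varying exposure depends mainly on how much person-time is vaccinated. That is set by the fraction vaccinated and by when vaccination happens. The SAPs print the timing and derive a single BNT162b2 fraction, yet the printed intervals are too narrow for that pair. Either Table 5.4 or one of the stated inputs must therefore be wrong.

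Table 5.4 is the only precision statement in the two VE SAPs, one of which serves the primary objective. A reader relies on it to judge which outcomes and subgroups can be informative.

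**Working it through.** **Inputs.** Follow-up runs from 11 September 2023 to 11 March 2024 (SAP 5.7.3), so T = 182 days. The BNT162b2 fraction is 288,000 / 3,000,000 = 9.6%. For adults it is 864,000 / 9,000,000 = 9.6%, or 864,000 / 8,550,000 = 10.1% if all doses fall in the simulated cohort. The other inputs are as printed in section 5.5. Vaccination is uniform from day 14 to day E, with E = 182 as stated.

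**1. Vaccinated share of person-time.** Ignoring censoring, the share is roughly fraction x (T - mean vaccination day) / T.
- 9.6%, E = 182: 0.096 x 84/182 = 4.4%
- 16%, E = 182: 0.16 x 84/182 = 7.4% (7.3% with censoring)
- 9.6%, E = 75: 0.096 x 137.5/182 = 7.3% (7.2% with censoring)
- 9.6%, E = 80: 0.096 x 135/182 = 7.1%

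**2. Interval widths.** Expected Cox information is the integral over follow-up of (event rate) x p(t)(1 - p(t)), where p(t) is the hazard-ratio-weighted vaccinated share of the risk set. Then SE = 1/sqrt(information), and the VE limits are 1 - HR x exp(±1.96 SE), in percent below.

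Example: 3,000,000 children, VE 20%, 50 per 100,000. The printed 2, 37 implies SE = ln(0.98/0.63)/3.92 = 0.113. The calculation gives 0.143 at 9.6% with the stated timing, 0.113 at 16%, and 0.113 to 0.114 at 9.6% with E = 75 or 80. Direct simulation with fitted Cox models (20 runs each) gave mean SEs of 0.144 at 9.6% as stated, 0.114 at 16%, and 0.114 at 9.6% finished by day 77.5.

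| N, VE, cases per 100,000 | Printed | 9.6%, E=182 | 16%, E=182 | 9.6%, E=80 |
|---|---|---|---|---|
| 3,000,000, 20%, 50 | 2, 37 | -6.0, 39.6 | 0.1, 35.9 | 0.0, 36.0 |
| 3,000,000, 20%, 100 | 7, 32 | 2.4, 34.4 | 6.4, 31.6 | 6.3, 31.7 |
| 3,000,000, 20%, 1000 | 16, 24 | 14.8, 24.9 | 15.9, 23.9 | 15.9, 23.9 |
| 750,000, 30%, 100 | 2, 50 | -6.9, 54.2 | 2.3, 49.9 | 2.0, 50.0 |
| 8,550,000, 20%, 50 | 7, 29 | 5.5, 32.3 | 8.8, 29.9 | 8.7, 29.9 |
| 2,137,500, 20%, 100 | 4, 34 | -1.2, 36.8 | 3.7, 33.6 | 3.5, 33.7 |

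Printed interval centres drift with simulation noise, so widths are the fair comparison. Over the 23 legible cells at 50 and 100 per 100,000 in both SAPs, printed SE / expected SE averages:
- 0.80 (0.78 to 0.83) at 9.6% as stated
- 0.82 at 10.1% as stated (11 adult cells)
- 1.01 at 16%
- 1.01 and 1.00 at 9.6% with E = 75 and 80
- 1.02 and 1.01 at 10.1% with E = 85 and 90 (adult cells)

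1/0.80 = 1.25 and 1/0.82 = 1.22, hence intervals about 25% and 22% wider than printed.

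**3. A check that does not use the intervals.** Raising VE from 20% to 40% removes events only from vaccinated time, so the relative fall in events measures the vaccinated share. At 10,000 per 100,000 and N = 3,000,000 the printed fall is (274,706 - 270,864)/274,706 = 1.40%. For 8.55, 0.75 and 2.14 million it is 1.49%, 1.35% and 1.47%. Expected falls are 0.86% (9.6% as stated), 0.90% (10.1%), about 1.44% (16%), 1.42% (9.6%, E = 75) and 1.40% (9.6%, E = 80). The 0.86% holds whether incidence is entered as a hazard or as a cumulative risk.

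**4. Other readings at about 9.6%.** Starting vaccination at day 0 or 28, a constant vaccination hazard, incidence as cumulative risk, T = 90 days, no censoring, and 10.3% uptake were each tried with vaccination continuing to the end of follow-up. The lower limit for the first cell stayed between -4.8 and -7.3, against 2 printed.

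**5. Replicates.** For the first cell, the Monte Carlo SE of a 10-run mean lower limit is 3.2 points at 16% (or 9.6% early) and 4.2 points at 9.6% as stated. At 500 runs these fall to 0.5 and 0.6. A 10-run lower limit lands above 0 with probability 0.59 at 16%, 0.57 at 9.6% early and 0.08 at 9.6% as stated. The printed 1488 events fit none of these inputs: the SE of a 10-run mean is about sqrt(1440/10) = 12, so 1488 is about 4 SEs above the expected 1440.

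**The case against.** The strongest reply is that 9.6% is never printed as a simulation input. It comes from a dose-count line, and 16%, printed in the same section, reproduces the table with the stated timing. On this view the defect is only an unstated input. That 16% fits is true. But the tables are titled for BNT162b2, the exposure is BNT162b2 only, and 9.6% is the only BNT162b2 fraction derived. If 16% was run, the table describes a different exposure. The early-completion explanation comes from fitting and appears nowhere in the text; it remains possible because the table cannot separate the two.

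Second, little depends on the table. The study is descriptive with a fixed data source. The uptake figures are extrapolations from BA.4/5. The Aim 2 SAP (10 June 2024) postdates the end of follow-up, so actual intervals will replace the projection. This stands, and it limits the importance of the point.

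Third, Louisiana will add precision. If its eligible share matches California's (3.8/19 million, about 20% more people), the adult subgroup limit becomes 0.8 at 9.6% or 1.3 at 10.1%. The pediatric cell still includes 0 at 9.6% (-3.4), though at 16% it rises to about 2. However, the concluding sentences are explicitly about the California registry, with Louisiana as an extra.

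Fourth, the additional pediatric subgroup cells that cross 0 (such as 750,000 at VE 30% and 100 per 100,000) arguably fall under the Aim 2 SAP's plural exception for rarer events. That is fair, and they are not counted here.

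**Conclusion.** The concern holds. Table 5.4 in both SAPs is inconsistent with 9.6% uptake and uniform vaccination to the end of follow-up. It is consistent with about 16%, or with 9.6% vaccinated by about day 75 to 80 (for adults, 10.1% by about day 85 to 90). The first conflicts with the BNT162b2 fraction and the second with the timing sentence. The documents do not settle which.

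If 9.6% and the stated timing are right, one of the 12 full-cohort pediatric cells includes 0. The adult subgroup cell at VE 20% and 100 per 100,000 becomes borderline (-1.2, 36.8 at 9.6%; -0.7, 36.4 at 10.1%), outside the single exception in the Aim 1 SAP. All other full-cohort cells still exclude 0; the smallest adult lower limit is 5.5 (5.9 at 10.1%). If early uptake was run, the tables stand apart from Monte Carlo error. Under any of these inputs, the full pediatric cell at VE 20% and 50 per 100,000 has a lower limit of about 0 or below, so the SAP's statement about it is not secure.

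These results assume 182 days of follow-up and the printed exponential and 5% censoring inputs. No estimand, model or reporting rule is affected.

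**What to change.** In section 5.5 of both SAPs, state the vaccinated fraction and the vaccination timing actually simulated, and whether censoring at another brand's vaccine is inside the 5%.

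- **If 16% was used:** rerun both tables at the BNT162b2 fraction (9.6%; for adults, 10.1% if all 864,000 doses fall in the 8.55 million). This costs 24 cells per SAP, two replaced tables and two revised concluding sentences.
- **If early uptake was used:** correct the timing sentence in each SAP and rerun only the borderline cells.

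In either case, use enough replicates that Monte Carlo error does not decide whether a limit crosses 0. About 500 runs bring it to 0.5 to 0.6 points in the cell examined. Then align the concluding sentences with the rerun, describing the full pediatric cohort at VE 20% and 50 per 100,000 as at best borderline in California. Run time depends on the replicates chosen. The only downside is a slightly less favourable statement of precision.
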